**A. Document type:**

Study Protocol with SAP.

**B. Background**

Smoking is a major risk factor of coronary artery disease (CAD) and is responsible for the death of one in three patients with cardiovascular diseases. Smoking cessation is one of the most favorable methods for reducing the risk of cardiovascular diseases; even for patients with a heart disease, quitting smoking can reduce the chance of a relapse of said disease. However, the Health Promotion Administration revealed that among male patients with acute myocardial infarction (AMI), 79.5% had smoked and 35.6% continued to smoke after an episode of AMI. Although previous studies confirmed that health education and exercises can increase smoking cessation rates, patients' lack of motivation to quit smoking has resulted in a failure rate of 65.5%. Therefore, identifying methods to strengthen patients' motivation to quit smoking is a key to successfully achieving smoking cessation.

## **C. Objective(s)**

The purpose of the study is to adopt the Trans-theoretical Model to facilitate step-by-step changes in a patient's smoking behavior and explore the effect of "Cognitive-Behavioral Education Course" and "Exercise Program" on Smoking cessation, physical health, and mental health of smokers with CAD.

## **D. Design and Methods**

There are three stages in our study, we will describe each stage as follow.

### **a. Stage 1:**

At this stage is a cross-sectional method and will be employed to investigate the relationship between smoking status and various physiological and psychological indicators in patients with CAD.

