### **b. Stage 2:**

At stage 2, subjects who are at the smoking cessation stage of "precontemplation" and "contemplation" will be recruited in this stage. A quasi-experimental design will be used to determine the effects of a four-week cognitive-behavioral education course related to smoking cessation on the participants' smoking cessation behavior, smoking decision-making, and self-efficacy in smoking cessation.

c. Stage 3:

Subjects who are at the "preparation" and "action" stage will be recruited and randomly divided into experimental or control group to identify the effect of a 12-week brisk walking on improving the participants' immediate (short-term), three-month, and six month (long-term) health status. The primary indicator used for health status evaluation is smoking cessation success rate; the secondary indicators used are physiological status (i.e., nicotine addiction, lung carbon monoxide concentration, heart rate variability, and smoking withdrawal syndrome) and psychological status (i.e., depression and

resilience).

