## **E. The statistical analysis**

SPSS for Window 24.0 software will be used in statistical analysis. The type one error is 0.05. In inferences analysis, chi-square test, Pearson correlation coefficient, independent t test, one-way ANOVA and post hoc comparison (scheffe) test will be used to examine the variance among groups. Finally, ANCOVA and GEE mode will be used to test the effectiveness of intervention respectively.

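### Stage 1 would be more informative with an age- and sex-adjusted regression beside its unadjusted tests (minor, cheap improvement)

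*Combined protocol and SAP*

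**What the plan says.** Section D, Stage 1, is a single sentence. It makes the stage cross-sectional, with the aim to "investigate the relationship between smoking status and various physiological and psychological indicators in patients with CAD". It describes no allocation and no intervention; the education course belongs to Stage 2 and the brisk walking to Stage 3.

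Section E is the whole analysis plan. For group comparisons and associations, "chi-square test, Pearson correlation coefficient, independent t test, one-way ANOVA and post hoc comparison (scheffe) test will be used". It then says that "ANCOVA and GEE mode will be used to test the effectiveness of intervention respectively". It attaches no method to a stage by number. No section names a covariate, or a regression, stratification or matching for Stage 1. Age is not mentioned anywhere. Sex appears only in a background figure in section B: "among male patients with acute myocardial infarction (AMI), 79.5% had smoked and 35.6% continued to smoke after an episode of AMI".

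Section C states the objective in terms of what the course and the exercise program do for "Smoking cessation, physical health, and mental health of smokers with CAD". The Stage 1 association question is not part of it.

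**The concern.** In an observational comparison nothing makes the smoking groups alike in age or sex. If they differ in either, and an indicator such as heart rate variability or depression also varies with it, an unadjusted difference mixes the two. A reader who sees only unadjusted results cannot tell whether an indicator is related to smoking among patients of the same age and sex, or whether the groups differ in who is in them.

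All the tests that section E leaves open to Stage 1 are unadjusted. The two methods that could take a covariate are assigned to the intervention question. What is at stake is the interpretation of the Stage 1 associations only.

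**Working it through.** **No figure to reproduce.** The documents give no sample size, effect size, SD or power for Stage 1. The check is a reading of the text, followed by illustrations on assumed inputs.

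**Text.** Stage 1 has no intervention, and ANCOVA and GEE are for testing the intervention. What remains for Stage 1 is chi-square, Pearson, t test and ANOVA with Scheffé, none of which adjusts for age or sex.

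**Illustration for sex.** Suppose there is no association within either sex, and a within-sex SD of 1. Then

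unadjusted difference = d × [P(woman | not exposed) − P(woman | exposed)],

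where d is the difference in the indicator between the sexes in SD units. It does not depend on the sample size.

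- *From section B:* 79.5% and 35.6%. These describe men with AMI; carrying them over to male CAD patients is an assumption.
- *Assumed:* 20–30% women; d = 0.2–0.5; 10–40% of women ever smoked; 5–20% of women smoke now.

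*Ever/never, mid case* (25% women, 20% of women ever smoked, d = 0.3):
- P(ever) = 0.75 × 0.795 + 0.25 × 0.20 = 0.646
- P(woman | ever) = 0.05 / 0.646 = 0.077; P(woman | never) = 0.20 / 0.354 = 0.565
- difference = 0.3 × 0.488 = 0.146 SD
- low (20%, 40%, 0.2): 0.062 SD; high (30%, 10%, 0.5): 0.301 SD

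*Current/not current, mid case* (25% women, 10% of women current, d = 0.3):
- P(current) = 0.75 × 0.356 + 0.25 × 0.10 = 0.292
- shares of women 0.086 (current) and 0.318 (not current); difference = 0.3 × 0.232 = 0.070 SD
- low (20%, 20%, 0.2): 0.023 SD; high (30%, 5%, 0.5): 0.165 SD
- if 35.6% is a share of ever-smokers, 0.356 × 0.795 = 28.3% of men smoke now, and the range is 0.014 to 0.146 SD

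*Current/former among ever-smokers* (men 35.6/79.5 = 44.8% or 35.6% still smoking; women assumed 20–60%): −0.074 to 0.075 SD if the share of women among ever-smokers follows from the rates above; −0.105 to 0.111 SD if 20–30% of the ever-smokers compared are women.

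All these differences are 0 if women's rates equal men's or if all participants are men.

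**Illustration for age.** The documents give nothing to anchor it, so every input is assumed. If the groups differ in age by d SD and age correlates r with the indicator within groups, the apparent difference is r × d. With no smoking association at a given age, n per group and a two-sided 0.05 level (section E gives 0.05 without sidedness), the chance of a significant result is P(|Z + r·d/√(2/n)| > 1.96):

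| d | r | r × d | n = 50 | n = 100 | n = 150 |
|---|---|---|---|---|---|
| 0.2 | 0.1 | 0.02 | 5.1% | 5.2% | 5.3% |
| 0.5 | 0.3 | 0.15 | 11.7% | 18.6% | 25.5% |
| 0.8 | 0.5 | 0.40 | 51.6% | 80.7% | 93.4% |

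**Price in precision (adjusting for sex).** Adjusted SE / unadjusted SE = 1/√[(1 − R²) × V]. R² is the squared correlation of smoking with sex, and V = 1 + d² × (average variance of sex within smoking groups); the sample size cancels. In the ever/never mid case R² = 0.290 and V = 1.012, so the ratio is 1/√(0.710 × 1.012) = 1.18. Over the assumed range it runs from 1.04–1.05 (unequal-variance or pooled SE) to 1.31. For current/not current it is 0.99 to 1.05, or 0.98 to 1.03 with 28.3% of men.

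**The case against.** The strongest reply is that this is silence, not an error. Stage 1 gets one sentence and section E maps no method to any stage, so the absence of adjustment is inferred from the tie between ANCOVA/GEE and the intervention. The unadjusted tests might even be meant for the Stage 2 and 3 groups, which would leave Stage 1 with no assigned analysis. That is fair, and it is why the point is limited to the plain reading. On either reading no adjusted analysis is assigned to Stage 1.

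Second, the aim is to look for a relationship, with no causal or independent-effect claim, and an unadjusted association answers that as a description. This stands, and it keeps the point minor.

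Third, age and sex are this review's choice of covariates, and the documents do not say whether women are enrolled. The illustrations also treat smoking as two groups, whereas ANOVA with Scheffé suggests three or more and Stage 2 classifies patients by cessation stage, for which the documents give no figures. This also stands: the numbers show what could happen and estimate nothing about this study.

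A reader might infer that the Stage 1 results are confounded or invalid. The documents do not support that, since they report no age or sex distribution by smoking group. Nor should the undefined meaning of smoking status, or the missing link between tests and stages, be counted as a wrong method; these are missing detail in a short plan.

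**Conclusion.** The point holds as a minor, inexpensive improvement. On the plain reading of section E, an observational comparison is left with unadjusted tests only, and an adjusted estimate beside them would tell the reader more.

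How far the associations reflect age or sex cannot be determined from the documents. With assumed inputs the illustrations run from nothing to about 0.30 SD for sex, and from negligible to large for age. The sex figures rest on an assumed share of women, assumed smoking rates in women, an assumed sex difference in the indicator, and male AMI rates applied to CAD.

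A reader might also take this as a weakness of the trial's main result. It is not: Stage 3 is randomised and does not rely on the Stage 1 tests, and Stage 1 lies outside the objective in section C.

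**What to change.** For each Stage 1 indicator, add a linear regression (continuous indicator) or logistic regression (binary indicator). Enter smoking status as a categorical exposure with its categories and reference level named, and age and sex as covariates (age only if all participants are men). Report the adjusted difference or odds ratio with a 95% CI beside the unadjusted result, and describe both as associations. If age and sex are not recorded, label the Stage 1 results as unadjusted and descriptive.

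The cost is one extra analysis per indicator in the same SPSS software, with no new patients or procedures. Age and sex must be recorded, which no section states. The interval usually becomes somewhat wider, by the ratios shown in the working, and now and then slightly narrower.

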### **b. Stage 2:**

At stage 2, subjects who are at the smoking cessation stage of "precontemplation" and "contemplation" will be recruited in this stage. A quasi-experimental design will be used to determine the effects of a four-week cognitive-behavioral education course related to smoking cessation on the participants' smoking cessation behavior, smoking decision-making, and self-efficacy in smoking cessation.

c. Stage 3:

Subjects who are at the "preparation" and "action" stage will be recruited and randomly divided into experimental or control group to identify the effect of a 12-week brisk walking on improving the participants' immediate (short-term), three-month, and six month (long-term) health status. The primary indicator used for health status evaluation is smoking cessation success rate; the secondary indicators used are physiological status (i.e., nicotine addiction, lung carbon monoxide concentration, heart rate variability, and smoking withdrawal syndrome) and psychological status (i.e., depression and

resilience).

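### Stage 3 randomises preparation and action patients as one pool, without specifying stratification by stage or stage as a covariate

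*Combined protocol and SAP*

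**What the plan says.** Section C builds the study on a stage model, to "adopt the Trans-theoretical Model to facilitate step-by-step changes in a patient's smoking behavior". Section D then sorts patients by stage. In Stage 2, "subjects who are at the smoking cessation stage of 'precontemplation' and 'contemplation' will be recruited in this stage", under a quasi-experimental design with an education course. The two later stages go to the randomised walking trial: "Subjects who are at the 'preparation' and 'action' stage will be recruited and randomly divided into experimental or control group".

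For that trial, "The primary indicator used for health status evaluation is smoking cessation success rate", assessed for "immediate (short-term), three-month, and six month (long-term) health status". Section E says "The type one error is 0.05" and that "ANCOVA and GEE mode will be used to test the effectiveness of intervention respectively". It lists no covariate, stage term or stratification factor, and does not say which of the two methods serves Stage 3. No result by stage is planned. The plan is silent on these points; it does not rule them out.

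**The concern.** Stage is the one baseline variable that the trial itself singles out. It decides which design and which intervention a patient receives, and in the underlying model it marks how far the patient has moved towards quitting, which is what the primary indicator measures. If action patients in the control arm succeed more often than preparation patients, three things follow from pooling them without stratifying or adjusting.

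- The variation between stages stays in the error term and power is lost.
- In the minority of trials where one arm happens to receive more action patients, the unadjusted difference shifts by the imbalance multiplied by the prognostic gap.
- A reader cannot see how each stage contributed to the pooled rate.

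Because no covariate is named in advance, the choice of adjustment can also be made after the data are seen.

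**Working it through.** **No plan figure to reproduce.** The documents give no sample size, power, effect size, allocation ratio or success rate by arm or stage. Only the type I error of 0.05 (section E) comes from the plan, and its sidedness is not stated. All else below is assumed for illustration: 1:1 allocation, n = 50 per arm, half the patients in action, a 20-point gain in both stages, a two-sided test and a single time point. Control success (preparation/action) is varied over four cases.

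**Power, unadjusted.** With pC and pT the pooled success rates, q = 1 − p, and pbar their mean:

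power = Φ{ [0.20 − 1.96·√(2·pbar·(1 − pbar)/n)] / √[(pC·qC + pT·qT)/n] }

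For 20%/70%: pC = 0.45, pT = 0.65, pbar = 0.55. The numerator is 0.20 − 1.96·√(0.495/50) = 0.20 − 0.195 = 0.005. The denominator is √(0.475/50) = 0.0975. Power = Φ(0.051) = 0.52.

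**Power, adjusted for stage.** Same formula, with the variances computed within stage and averaged. For 20%/70%:

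- Null variance: preparation 0.30 × 0.70 = 0.21, action 0.80 × 0.20 = 0.16, mean 0.185. Critical value 1.96·√(2 × 0.185/50) = 0.1686.
- Alternative variance: preparation 0.16 + 0.24 = 0.40, action 0.21 + 0.09 = 0.30, mean 0.35. Standard error √(0.35/50) = 0.0837.
- Power = Φ[(0.20 − 0.1686)/0.0837] = Φ(0.375) = 0.646.

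| Control success, preparation/action | Outcome variance explained by stage | Power unadjusted | Power adjusted |
|---|---|---|---|
| 30%/40% | 1.1% | 0.520 | 0.525 |
| 25%/45% | 4.4% | 0.520 | 0.537 |
| 20%/60% | 16.7% | 0.516 | 0.590 |
| 20%/70% | 25.3% | 0.520 | 0.646 |

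At 100 per arm the same formula gives 0.82 unadjusted and 0.82 adjusted for 30%/40%, and 0.82 against 0.91 for 20%/70%. Simulated logistic models at 50 per arm agree closely: 0.54 unadjusted, 0.53–0.54 adjusted at 30%/40%, and 0.64–0.67 adjusted at 20%/70%.

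**Chance imbalance.** At 50 per arm with simple randomisation, a gap of at least 20 points in the action share arises in 5.7% of trials if half the patients are in action, and in 3.8% if 30% are. If exactly half of all enrolled patients are in action, the figure is 7.1% at 50 per arm, 34% at 20, 20% at 30 and 0.7% at 100. A 20-point imbalance shifts the unadjusted difference by 0.20 × gap: 2 points at 30%/40% and 10 points at 20%/70%.

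**Type I error.** Simulated with no treatment effect, 50 per arm:

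- Over all trials, unadjusted: 4.5–5.6%.
- In trials with an imbalance of at least 20 points, unadjusted: about 5–6% (30%/40%), 7% (25%/45%), 14% (20%/60%) and 19% (20%/70%).
- In the same trials, adjusted for stage: about 5%.

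**Stratifying without adjusting.** Type I error becomes 2·{1 − Φ[1.96·√(Vpooled/Vwithin)]}. At 20%/70%, Vpooled = 2 × 0.45 × 0.55 = 0.495 and Vwithin = 0.16 + 0.21 = 0.37, giving 2.3%. At 30%/50% it is 4.5%. The test is then conservative, so stratification and adjustment belong together.

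**Odds ratio.** A within-stage odds ratio of 2 corresponds to a marginal odds ratio of 1.98, 1.94, 1.77 and 1.68 in the four cases. That is non-collapsibility, not bias, but the two quantities are different.

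**The case against.** Simple randomisation with an unadjusted comparison is valid, so nothing in the plan is wrong in the strict sense. That stage is prognostic is an inference from the trial's model, because no document gives success by stage. The only related figure is the 65.5% failure rate in section B, which means about 34.5% success (100 − 65.5). The 30%/40% and 25%/45% cases average 35%, and their power gains are only 0.4 and 1.7 points. The large gains need differences of 40 to 50 points between adjacent stages, which nothing in the documents supports. The 19% figure is conditional: imbalanced false positives in that case are 0.057 × 0.193 = 1.1% of all trials. The illustration tests two proportions at one time point, whereas the plan has three time points and names GEE. Finally, ANCOVA normally carries a covariate and GEE can carry stage.

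Most of this stands and limits the emphasis. The gain may be close to zero, and 13 points is an extreme, not an expectation. The section B figure comes from earlier studies and is not split by stage, so it does not exclude a wide gap either. That the models could carry stage does not commit anyone to including it. None of these points gives a reason to leave out a prognostic candidate that the trial already records before allocation.

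**Conclusion.** The concern holds. Stage 3 pools two stages of change, and the plan specifies neither stratified allocation nor a stage covariate, although stage is known at recruitment and the trial's own model makes it a likely predictor. The comparison remains unbiased, with overall type I error near 5%. The cost is precision: between almost nothing and about 13 points of power at 50 per arm, depending on how far control success differs by stage. There is also an avoidable sensitivity to chance imbalance, which matters more the smaller the trial. Sample size, stage mix, effect and success rates are all assumed, so confidence in the size is moderate. The change should be made, but the trial is valid without it.

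**What to change.** In section D, Stage 3, state that randomisation is stratified by baseline stage (preparation or action). In section E, name the model for the Stage 3 success rate, for example the GEE, and include baseline stage as a covariate. If the result is an odds ratio, say whether it is marginal or conditional. Report success by stage and arm as a descriptive secondary result. If allocation has already taken place, add the covariate and the descriptive split only, and record this before the outcome data are examined.

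The cost is one stratification factor, one covariate and one sentence on the odds ratio. No extra patients or measurements are needed. If stage proves weakly prognostic, the gain will be close to zero.

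### Must Stage 3 name the one time point or GEE term that decides success on smoking cessation?

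*Combined protocol and SAP*

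**What the plan says.** Under Design and Methods, item c (Stage 3), patients in the preparation and action stages are randomised to experimental or control group to "identify the effect of a 12-week brisk walking" on "immediate (short-term), three-month, and six month (long-term) health status. The primary indicator used for health status evaluation is smoking cessation success rate". The physiological and psychological measures are secondary. So there is one primary indicator, assessed at three times, with none singled out.

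The Objective(s) section states the aim as the effect of the education course and the exercise programme "on Smoking cessation, physical health, and mental health of smokers with CAD", without a time.

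Section E sets the error rate ("The type one error is 0.05"), lists general between-group and correlation methods ("chi-square test, Pearson correlation coefficient, independent t test", among others), and ends by saying that "ANCOVA and GEE mode will be used to test the effectiveness of intervention respectively". It gives no GEE term, no contrast, no statement on whether baseline is in the model, and no rule for combining the three times.

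**The concern.** GEE is a way of estimating, not a hypothesis. Fitted to three repeated assessments, it can deliver a group effect averaged over visits, a joint test of any group difference across visits, a contrast at one visit, or a group-by-time term. These answer different questions and need not agree on the same data. The chi-square test in the same section also leaves room for separate comparisons at each visit.

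Stage 3 is the only randomised part of the study, so its primary comparison carries the strongest causal claim. If walking helped patients stop smoking at first but the benefit had gone by six months, one permitted reading would call that a success and another a failure. A reader could not tell from the plan which was intended. The time origin is also unstated: three and six months could run from enrolment or from the end of the programme.

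**Working it through.** **No figure to reproduce.** The documents give no sample size, power, effect size or within-person correlation. The only design number is the 0.05 in section E, taken here as two-sided (assumed).

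**Set-up.** Let Z1, Z2, Z3 be the group-comparison statistics at the three times, each with variance 1 and pairwise correlation ρ. Assumed ρ = 0.5, 0.8 and 0.9. A mean of 2.80 gives 80% power at one time, since 1.96 + 0.84 = 2.80.

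**Error rate.** With no effect, the single-time, averaged, 3-df joint and 2-df group-by-time tests each reject in 5.0% of simulated trials at every ρ. Inflation appears only if any one of three separate tests may count, a rule the plan does not state. Counting false claims of benefit only, the rate would then be 1 − 0.975³ = 7.3% at ρ = 0 and 6.3/4.9/4.2% at ρ = 0.5/0.8/0.9, against 2.5%.

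**Steady effect, means (2.8, 2.8, 2.8).** The averaged test has mean 2.8 × √[3/(1 + 2ρ)]:

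- ρ = 0.5: 2.8 × 1.225 = 3.43, power Φ(3.43 − 1.96) = 93%
- ρ = 0.8: 2.8 × 1.074 = 3.01, power 85%
- ρ = 0.9: 2.8 × 1.035 = 2.90, power 83%

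The joint test has non-centrality 3 × 2.8²/(1 + 2ρ) = 11.8/9.0/8.4, hence power 83/71/68%. The group-by-time term over the three follow-ups has non-centrality zero, hence 5%. If baseline is a time level in the model, that term means something different and this last figure does not apply.

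**Disagreement.** Share of trials in which the six-month, averaged and joint tests do not all agree, for a steady effect:

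| Power at each time | ρ = 0.5 | ρ = 0.8 | ρ = 0.9 |
|---|---|---|---|
| 50% | 34% | 28% | 25% |
| 80% | 20% | 20% | 20% |
| 90% | 11% | 13% | 13% |
| 95% | 6% | 8% | 8% |

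The set of tests matters too: at 80% power, six-month against averaged alone disagree in 15/9/6%.

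**Effects that wane, 80% power at the immediate time.** If the effect halves by six months (means 2.8, 2.1, 1.4), the three tests fail to agree in 53/54/63% of trials. If it vanishes (2.8, 1.4, 0), they fail to agree in 79/96/97%, with power 5% at six months, 40/32/30% averaged and 80/98/100% joint.

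**Check with binary data.** The control success rate was assumed to be 100 − 65.5 = 34.5%, from the Background ("has resulted in a failure rate of 65.5"), which is not a design input. With an assumed 54.5% on treatment and 93 per arm, the standard error is √[(0.345 × 0.655 + 0.545 × 0.455)/93] = 0.0714, and 0.20/0.0714 = 2.80. With within-person correlation 0.50 and 0.79, simulated power was 78/78% at six months, 92/85% averaged and 82/70% joint. The three did not all agree in 22/21%, in line with the table.

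**Clock.** From programme end, the later visits fall at about weeks 12 + 13 = 25 and 12 + 26 = 38. From enrolment, they fall at about weeks 13 and 26. On the second reading the three-month visit nearly coincides with the immediate one at week 12, so the first reading is the natural one.

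**Which method for which stage.** Two stages have an intervention and two methods are named in order. Stage 2 comes first and Stage 3 has the repeated follow-ups, so the closing sentence of section E most naturally gives ANCOVA to Stage 2 and GEE to Stage 3.

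**The case for a change.** The strongest case for a change is that the document calls itself a protocol with SAP, and naming the primary test is a core task of a SAP. No other section fills the gap, and section E reads as a complete paragraph, so redaction does not explain it. Adding a sentence would need no patients or visits. If the effect wanes, the permitted tests disagree more often than not under the assumptions above.

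Much of this stands. The omission is a fact, and a named contrast would make the report easier to trust. What does not stand is the step from there to a flaw in the method. The waning cases show tests answering different questions correctly: a six-month test should find nothing when nothing is left at six months, and a joint test should find an early effect. Nor is there a single correction to ask for. The averaged test loses power when the effect fades (40/32/30%). The joint test gives up power when it is steady (83/71/68% against 93/85/83%) and does not say when or in which direction the groups differ. A single named time gives no primary claim for an effect at another time. Which loss to accept depends on what the sponsor wants to learn.

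**Conclusion.** This is a gap in detail that calls for no change to the plan. The plan has one primary indicator, a randomised comparison, an analysis method suited to repeated assessments and a 5% error rate. An analyst can fill in the rest with any one of three valid contrasts, provided it is settled before the results are seen. Nothing in the text permits counting the best of three tests, so the inflation to 6.3/4.9/4.2% belongs to a rule that the plan does not contain.

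The often-quoted size, disagreement in about one trial in five, is not a property of this trial. It holds for one chosen set of three tests at an assumed 80% power per time. For a steady effect the same set gives about 6 to 34% as power runs from 95% down to 50%, and more if the effect wanes. These figures also assume a two-sided test, equal correlation between visits and approximately normal statistics. The time origin is a minor wording point with one natural reading. A reader of the eventual report should check which contrast was used and whether all three times are shown.
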